BIOMEDICAL RESEARCH PROTOCOL UNIVERSITY OF MISSOURI

Project Title: Estrogen receptor alpha signaling in endothelial cells exacerbates arterial

stiffening via upregulation of ENaC in insulin resistant females

IRB Number: 2012990 Version Number: 24

Version Date: October 30, 2023

Principal Investigator: [name]

Funding Source: NHLBI

Clinical Trial Phase: Phase II

Clinicaltrials.gov Number: NCT03837626 Study Drug/Study Device: *Amiloride*

I. Research Objectives/Background

Hypothesis: Estrogen action, through the endothelial cell (EC) estrogen receptor alpha (ERα) upregulates EC ENaC expression and activity exacerbating endothelial and arterial stiffening in overweight and obese, insulin resistant (IR) premenopausal females. The corollary to this hypothesis is that ENaC inhibition will have a greater impact on arterial stiffness in overweight and obese, premenopausal insulin resistant women than in overweight and obese IR postmenopausal women or age matched obese IR men.

To test our hypothesis, we will use in vivo measures of endothelial function and arterial stiffness in a cohort of overweight and obese IR subjects treated with amiloride, an ENaC inhibitor, to accomplish the follow aim:

To determine whether treatment with the ENaC inhibitor, amiloride, improves endothelial function and arterial stiffness in overweight and obese IR subjects in a randomized placebo-controlled trial examining pre and postmenopausal women and age-matched men.

II. Drugs/Biologics/Devices

Following screening, male and female subjects will be randomized to a doubled blinded placebo control trial. Subjects will start on either a 24-week treatment with oral medication, either amiloride, a max dose of 5 mg daily, or placebo intervention.

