- 9. Participation in regular exercise > 3 days/wk per week at a moderate or vigorous intensity
- 10. Pregnancy or lactation in women (or women not using contraceptives)
- 11. Women who plan to become pregnant during the duration of the trial
- 12. Chronic use of NSAIDs
- 13. Potassium level > 5.0 mqE/L at time of screening
- 14. Blood pressure at screening <110/70

VI. Number of Subjects

Men (n=72) and women (n=87) (total=159 overweight/obese subjects) with IR will be recruited for this study. Postmenopausal women are those who have not menstruated for at least **6 months**.^{5,6}

Table 1 presents the estimated sample sizes necessary to test the response to amiloride and compare the

[figure not shown]
Table 1. Repeated- measures design for amiloride treatment	Baseline and treatment cfPWV (m/s)	SD of the Δ	Power	Alph	Calculated sampled size	Final recruitment target 2:1 Amiloride Placebo	
1. Premenopausal women	7.2> 6.2	1.2	90%	0.05	30	34	17
2. Young men (30-50 y)	7.1> 6.6	0.5	90%	0.05	21	24	12
3. Old men (51-70 y)	8.0> 7.5	0.5	90%	0.05	21	24	12
4. Postmenopausal women	8.0> 7.5	0.5	90%	0.05	21	24	12

responses of men and women. We hypothesize that the improvement in carotid femoral pulse wave velocity (cfPWV) in men will be intermediate between the two female groups. Because of the negative effect of estrogen-stimulated ENaC activation, we believe that amiloride will benefit premenopausal women more (a Δ , reduction of 1.0 m/s) than the other groups. Our sample size also allows for a greater variation in the response of premenopausal women due to the effects of reproductive hormones in this group⁷ (SD of the change of 1.2 m/s, **Table 1**). By contrast, we anticipate that the response of post-menopausal women (**Table 1**) will be equal to that of the older men or could even be the lowest of all the groups, given a lesser contribution of estrogen signaling in the activation of ENaC in this population. In summary, the final sample sizes listed below will give 90% power to detect each group's changes in cfPWV.

VII. Study Procedures/Design/Treatment Plan

Planned visits:

Screening visit: Written consent, DOB, gender, ethnic/racial category, height, waist circumference, body weight (history of body weight gain or loss, vital signs, medical history and screening laboratories. Entire visit

is expected to take up to an 1 hour.

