**STATISTICAL ANALYSIS PLAN
UNIVERSITY OF MISSOURI**

Project Title: Estrogen receptor alpha signaling in endothelial cells exacerbates arterial stiffening via upregulation of ENaC in insulin resistant females

IRB Number: 2012990

Version Date: November 13, 2025

Principal Investigator: [name]

Funding Source: **NHLBI**

Clinical Trial Phase: *Phase II*

Clinicaltrials.gov Number: NCT03837626

Study Drug/Study Device: *Amiloride*

Statistical analysis plan – primary outcome

Linear mixed-effects models were used to evaluate changes in continuous outcome variables. Each outcome was analyzed in a separate model using the **lmer** function in the *lme4* package (R Foundation for Statistical Computing). Fixed effects included time, group, and their interaction (time \times group). A random intercept for participant ID was included to account for within-participant correlation from repeated measurements. Models were estimated using restricted maximum likelihood (REML).

Model assumptions were examined and satisfied, including assessment of normality of residuals, homogeneity of variance, multicollinearity, and evaluation for singular fit. Missing data were handled by the default behavior of **lmer()**, which excludes observations containing NA values; no imputation was performed.

Continuous data were visualized using GraphPad Prism (version 10.0) and are presented as mean values with 95% confidence intervals. Because only two groups were compared, no correction for multiple comparisons was applied.

Significance as set as $p \leq 0.05$.

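### The SAP leaves *group* undefined; read as treatment arm, its model gives no estimate of the hypothesised larger amiloride effect in premenopausal women

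*SAP*

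**What the plan says.** **Hypothesis.** Protocol section I expects a greater effect on arterial stiffness in "premenopausal insulin resistant women than in overweight and obese IR postmenopausal women or age matched obese IR men". It presents the trial as the means of examining this: "To test our hypothesis, we will use in vivo measures of endothelial function and arterial stiffness". The aim that follows is whether amiloride improves endothelial function and stiffness in a "randomized placebo-controlled trial examining pre and postmenopausal women and age-matched men".

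**Sample size.** Protocol section VI introduces Table 1 as giving the "estimated sample sizes necessary to test the response to amiloride and compare the" "responses of men and women", and adds that "we believe that amiloride will benefit premenopausal women more". Table 1 has four strata with 2:1 targets:

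| Stratum | Planned change (m/s) | SD of change | Amiloride : placebo |
|---|---|---|---|
| Premenopausal women | 1.0 | 1.2 | 34 : 17 |
| Men 30-50 y | 0.5 | 0.5 | 24 : 12 |
| Men 51-70 y | 0.5 | 0.5 | 24 : 12 |
| Postmenopausal women | 0.5 | 0.5 | 24 : 12 |

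The 90% power claimed there is for each group's own change in cfPWV, not for a difference between groups.

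**Analysis.** The SAP specifies "Fixed effects included time, group, and their interaction", with a random intercept per participant and REML. It then says: "Because only two groups were compared, no correction for multiple comparisons was applied". It names no sex, menopausal or age-stratum term, no fits by stratum and no contrast between strata. The protocol has no analysis section that supplies one.

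**The concern.** The trial has two arms and four strata, and the SAP's one grouping variable has two levels. The natural reading is that *group* is the treatment arm. The time × group coefficient is then a single amiloride-versus-placebo effect averaged over whoever was enrolled, and no quantity in the SAP measures how that effect differs between premenopausal women and the others.

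The study's title and opening hypothesis concern exactly that difference. Without a stated contrast, a report could present the pooled effect as support for it, or compare significance from one stratum to the next. Neither answers the question. The SAP proposes neither, but it leaves room for both.

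**Working it through.** **Inputs.** Changes, SDs and targets are from Table 1. Assumed here: zero mean change on placebo, equal SD in both arms, all four strata filled at 2:1, two-sided alpha 0.05. Figures use the normal approximation unless marked t.

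**Step 1: reproduce Table 1.** The two-sample formula per arm at 1:1 is n = 2 × [SD × (1.960 + 1.282)/Δ]².
- Premenopausal: 2 × (1.2 × 3.242/1.0)² = 30.3; the table says 30.
- Other strata: 2 × (0.5 × 3.242/0.5)² = 21.0; the table says 21.

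The inputs are therefore understood as the protocol used them.

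**Step 2: what the pooled coefficient shows.** With 2:1 allocation in every stratum, its expected value is the enrolment-weighted mean effect: (34 × 1.0 + 72 × 0.5)/106 = 70/106 = 0.66 m/s. A uniform effect of 0.66 gives the same value. Simulation of change scores under each pattern gave a mean of 0.66, an SE of about 0.13 and power of 99.8% in both cases. With no effect in any stratum, the type I error was 4.9%. The pooled test is sound, but it cannot tell the hypothesised pattern from equal effects.

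**Step 3: what separate stratum tests show.** SE = SD × sqrt(1/nA + 1/nP).
- Premenopausal: 1.2 × sqrt(1/34 + 1/17) = 0.356; expected z = 1.0/0.356 = 2.81.
- Each other stratum: 0.5 × sqrt(1/24 + 1/12) = 0.177; expected z = 0.5/0.177 = 2.83.

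Power is 80-81% (about 78.5% with t) in every stratum, although the premenopausal effect is twice as large. The pattern of p-values would look alike across strata and would say nothing about the difference.

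**Step 4: the contrast that answers the hypothesis.** For premenopausal minus postmenopausal women, or premenopausal women minus men 30-50 y:
- SE = sqrt(0.356² + 0.177²) = 0.398 m/s.
- CI half-width = 1.96 × 0.398 = 0.78 (0.79 with t).
- Planned difference = 1.0 − 0.5 = 0.5 m/s; z = 0.5/0.398 = 1.26; power 24% (23% with t).
- With Holm over the two contrasts, which share the premenopausal estimate (correlation 0.80), power is 18-19% for each.
- Difference detectable with 80% power = 2.80 × 0.398 = 1.11 m/s.

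**Step 5: sensitivity.** Protocol section X cites retention above 85% in the team's earlier studies.
- At 85%, SE = 0.398/sqrt(0.85) = 0.432. With whole numbers (29:14 and 20:10) it is 0.436. Power is about 20-21%, and 80% power needs 1.21-1.22 m/s.
- If the premenopausal SD were 0.8 instead of 1.2, SE is 0.296 and power 39%. If it were 0.5, SE is 0.231 and power 58%.

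**The case against.** **The stated aim is only whether amiloride improves stiffness, and the model answers it.** This stands. Section I calls the differential effect a corollary, the SAP is headed as covering the primary outcome, and it makes no claim of effect modification. Harm arises only if such a claim is made later. This limits the severity. It does not remove the gap, because section I puts the hypothesis first and section VI says the sizes serve to compare responses.

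***Group* might not mean arm.** This also stands in part. Section VI uses the word for the strata. If *group* meant two strata, time × group would be a between-stratum contrast, but the comparison with placebo would be absent. It is also possible that only some strata were analysed; the documents give recruitment targets but no accrual. Each reading needs a clarification, so the missing contrast is stated here only for the natural reading.

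**The added contrast is imprecise and late.** True. The SAP is dated November 2025 and written in the past tense, so the contrast would have to be reported as a later addition, and SAP wording cannot repair the design's size. That is a reason to show the estimate with its interval, not to leave the hypothesis without one.

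**Stronger readings.** A reader might infer that the pooled amiloride-versus-placebo result is invalid, or that it needed a multiplicity correction. The documents do not support this: a single two-arm comparison is valid, as Step 2 shows. A reader might also infer that the protocol promised 90% power for the difference between strata. It did not; that claim covers each group's own change.

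**Conclusion.** The point holds in a limited form and should be fixed. *Group* is undefined. If it means arm, following the SAP exactly yields no estimate of the difference that the protocol hypothesises, and the pooled 0.66 m/s carries no information about it. If it means two strata, the placebo comparison is what is missing. The pooled amiloride-versus-placebo result is not undermined, provided that allocation is about 2:1 in each stratum, as Table 1 targets.

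The sizes rest on Table 1's inputs, zero placebo change, equal SDs across arms and full strata. If a stratum did not fill, they would be worse. The contrast needs no new data, but at about one chance in four of detecting the planned difference (one in five with Holm) it can only be read as an estimate.

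**What to change.** 1. Define *group* as treatment arm, limit the two-groups sentence to the pooled comparison, and state the numbers analysed per stratum and arm.
2. For the strata actually enrolled, fit the SAP's lmer model separately in each, with time as a categorical factor (the SAP does not say how time is coded). Report the week-24 amiloride-minus-placebo difference in cfPWV change with 95% CI. Separate fits also let the variance differ by stratum, as Table 1 anticipates.
3. Report two differences between these estimates with 95% CI, using SE = sqrt(SE1² + SE2²): premenopausal minus postmenopausal women, and premenopausal women minus age-matched men. The latter are assumed here to be Table 1's 30-50 y stratum; the SAP should confirm or replace that choice. If the differences are tested, use a multiplicity adjustment such as Holm.
4. Label these contrasts as added after the SAP of 13 November 2025, and do not read a non-significant result as equal effects.
5. Base any claim of greater premenopausal benefit on these contrasts alone, or state that no such claim will be made.

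**Cost.** At most four fits of the existing model, two subtractions and some SAP wording, with no new subjects or visits. The price is wide intervals: if Table 1 is exactly right, each Holm-adjusted contrast would still be non-significant about four times in five. If a stratum did not fill, its contrast is less precise or cannot be made, and the report should say so. The cheapest alternative is one sentence ruling out a claim of effect modification.

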- Visit #1: Vital signs (blood pressure and heart rate), weight, DEXA, assessment of brachial and popliteal artery flow-mediated dilation (FMD), cfPWV, femoral artery blood flow, and oral glucose tolerance test (OGTT) (amount of blood drawn not exceeding 55 mL). OGTT will be done when glucose beverage is available. Entire visit is expected to take up to 6 hours. Women of childbearing age will undergo a pregnancy test prior to the DEXA scan and excluded if pregnancy is confirmed. Subject is dispensed the bottle of study drug/placebo and instructed how to take them.
- Visit #2 (1 week after starting the medication +6 days/-2 days): Vital signs, safety questionnaire for side effects, and blood draw for safety laboratories (basic metabolic panel). Entire visit is expected to take up to 30 minutes.
- Visit #3 (4 weeks after starting the medication +/- 6 days): Vital signs, safety questionnaire for side effects, and blood draw for safety laboratories (basic metabolic panel). Entire visit is expected to take up to 30 minutes.
- Visit #4 (8 weeks after starting the medication +/- 6 days): Vital signs, safety questionnaire for side effects, and blood draw for safety laboratories (basic metabolic panel). Entire visit is expected to take up to 30 minutes. If the prior safety visit labs have been within the protocol parameters this visit may be completed as a phone call visit to collect safety questionnaire for side effects and any changes in the subject's health.
- Visit #5 (12 weeks after starting the medication +/- 6 days): Vital signs, weight, DEXA, safety questionnaire for side effects, and blood draw for safety laboratories (basic metabolic panel) and general biochemistries. Subject also will have assessment of brachial and popliteal artery FMD and cfPWV. Women of childbearing age will undergo a pregnancy test prior to the DEXA scan and withdrawn from study if pregnancy is confirmed. Subject will be dispensed a new bottle of study drug/placebo. Entire visit is expected to take up to 3 hours.
- Visit #6 (16 weeks after starting the medication +/- 6 days): Vital signs, safety questionnaire for side effects, and blood draw for safety laboratories (basic metabolic panel). Entire visit is expected to take up to 30 minutes. If the prior safety visit labs have been within the protocol parameters this visit may be completed as a phone call visit to collect safety questionnaire for side effects and any changes in the subject's health.

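### The SAP's reason for making no multiplicity correction (only two groups) does not cover several outcomes or visits, and no primary outcome, visit or contrast is named

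*SAP*

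**What the plan says.** The SAP is one page under the heading "Statistical analysis plan – primary outcome", in the singular. The text below the heading names no outcome variable, visit or contrast. On the models it says "Each outcome was analyzed in a separate model", and "Fixed effects included time, group, and their interaction". The significance threshold is p ≤ 0.05. On multiplicity its only statement is "Because only two groups were compared, no correction for multiple comparisons was applied".

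The protocol (section I) gives a single aim: to find out whether amiloride "improves endothelial function and arterial stiffness in overweight and obese IR subjects in a randomized placebo-controlled trial". Section I also states a corollary, that the effect will be larger in premenopausal women than in postmenopausal women or men. Section VI, Table 1, sizes the trial on cfPWV alone, separately for four groups: premenopausal women, young men, older men and postmenopausal women.

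Section VII measures brachial FMD, popliteal FMD and cfPWV at baseline (Visit #1), at week 12 (Visit #5: "Subject also will have assessment of brachial and popliteal artery FMD and cfPWV") and again at week 24 (Visit #8). The protocol does not designate a primary endpoint either.

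**The concern.** The number of arms settles only how many arm-to-arm comparisons there are for one outcome at one time. With amiloride and placebo there is one, so no pairwise correction is needed. That says nothing about testing three vascular measures, or one measure at two follow-up visits. The SAP offers the first fact as the reason to ignore the second.

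This would matter little if one test had been named as primary, because the rest would then be secondary and the reader could weigh them so. Here nothing marks which result answers the aim. A significant brachial FMD result at week 12 and a significant cfPWV result at week 24 have the same formal standing, and a reader of the final report could not tell whether the result put forward was the one intended.

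The phrase about two groups also leaves the planned sex and menopause comparisons unaccounted for. They are the protocol's corollary hypothesis and the basis of Table 1, yet the SAP neither includes them in its count of comparisons nor says that they were dropped.

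**Working it through.** **What the plan states.** There is no familywise error rate in either document to reproduce. The only stated figure is the per-test threshold of 0.05. For one named test the error rate is 1 − 0.95 = 5%.

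**Inputs from the documents**
- Level per test: 0.05 (SAP). Sidedness is not given; two-sided is assumed.
- Vascular outcomes named by the aim and measured at both follow-up visits: brachial FMD, popliteal FMD and cfPWV, so 3 (protocol sections I and VII).
- Post-baseline visits with these measures: weeks 12 and 24, so 2.
- Adjustment: none (SAP).

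**Inputs not in the documents (assumed)**
- Whether time-by-group is one joint test per outcome (3 tests) or separate week-12 and week-24 contrasts (3 × 2 = 6 tests).
- Correlation r between test statistics, taken from 0 to 0.7.
- A rule that any one significant result counts as meeting the aim.

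**Formula.** For k independent tests, P(at least one false positive) = 1 − 0.95^k.
- k = 2 (cfPWV at two visits): 1 − 0.95^2 = 9.8%
- k = 3: 1 − 0.95^3 = 14.3%
- k = 6: 1 − 0.95^6 = 26.5%

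For k two-sided normal statistics with a common correlation r, the probability is 1 − ∫ φ(x) [Φ((1.96 − √r·x)/√(1−r)) − Φ((−1.96 − √r·x)/√(1−r))]^k dx. Numerical integration gives:

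| r | 3 tests (one joint test per outcome) | 6 tests (outcome by visit) |
|---|---|---|
| 0 | 14.3% | 26.5% |
| 0.3 | 13.6% | 24.1% |
| 0.5 | 12.5% | 20.7% |
| 0.7 | 10.9% | 16.4% |

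For correlated joint tests, which may have more than one degree of freedom, the normal model is an approximation. The independent figure of 14.3% is exact.

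A more structured pattern stays inside the six-test range. With correlation 0.5 between visits and 0 to 0.5 between outcomes, simulation gives 24.8% down to 21.9%.

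**The two-groups statement against Table 1.** The recruitment targets, amiloride plus placebo, are 34 + 17 = 51 premenopausal women and 24 + 12 = 36 in each of the other three groups. The total is 51 + 3 × 36 = 159. The design therefore has two arms within each of four groups, and the corollary hypothesis compares those groups. A count of two describes the arms only.

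**The case against.** The strongest reply is that cfPWV is already the primary outcome in all but name. The SAP heading is singular, Table 1 uses cfPWV alone, and the study title and the corollary concern arterial stiffness. With one cfPWV contrast the error rate is 5%, and other outcomes in a Phase II mechanistic trial need no correction. Much of this stands: the documents do point to cfPWV, which is why it is the natural choice in the fix. But neither document says so, and the visit would still be open. Two cfPWV tests give up to 9.8%.

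A second reply is that the aim joins its two parts with "and". If both had to succeed, with one test for each, the chance of a false claim would not exceed 5%. That is fair. The documents state neither that rule nor the opposite one, so the any-one-result rule behind the figures above is an assumption.

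A reader might also go further and infer that the SAP runs six tests at 0.05, that the false-positive chance is therefore in the low to mid twenties per cent, and that this breaks a promised 5%. The documents do not support that. The SAP lists no outcomes, does not describe per-visit tests, gives no correlations, and sets 0.05 as a per-test threshold without claiming a familywise rate.

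**Conclusion.** The concern holds in this form: the stated rationale is wrong, and the primary test is not named. Both follow from the text alone and need no assumption.

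The size is conditional. If any one significant result were taken as meeting the aim, the chance of at least one false positive would be about 11–14% with three joint tests and about 16–26% with six separate tests, for correlations from 0.7 down to 0. Either range is at least twice 5%, and the SAP does not let a reader tell which applies. For a single named cfPWV contrast the figure is 5%. This should be corrected, but it does not show that any particular result is false.

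**What to change.** Delete the sentence about two groups and replace it with text such as:

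*The primary test is the amiloride-versus-placebo difference in change in cfPWV from baseline to week 24, two-sided at 0.05. Week-12 cfPWV, brachial and popliteal FMD, and comparisons between the sex, menopause and age groups are secondary. They are either Holm-adjusted within a listed family, or reported as estimates with 95% confidence intervals and no claim of significance.*

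cfPWV at week 24 is the natural choice because cfPWV is the only outcome used for the sample size and 24 weeks is the treatment length. The text should not say that Table 1 powers this contrast: Table 1 concerns cfPWV change within each of four groups, and names neither a pooled comparison nor a visit.

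The SAP is dated November 13, 2025 and is written in the past tense, with model assumptions already reported as satisfied. A primary test named now must cite an earlier dated record of that choice or be labelled post hoc. The SAP should also say whether time-by-group is tested jointly or by visit, and what "group" means in the model.

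The cost is some redrafting and a search for the earlier record. FMD and week-12 results lose an unadjusted significant label. If Holm is used for week-12 cfPWV and the two FMD measures at two visits (1 + 2 × 2 = 5 tests), the smallest p-value is compared with 0.05/5 = 0.01, and with a lower value once group comparisons are added.
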